3.1.1. RADIOGRAPHIC SUCCESS

The proportion of radiographically successful knees in the Cementless group is non-inferior to the proportion of radiographically successful knees in the Control group using an 8% margin of non-inferiority. The test is based on the upper bound of a one-sided 95% confidence interval for the difference, Control minus Cementless, of proportions of success at 22+ months. A conclusion of non-inferiority is supported if the upper bound of the confidence interval is 0.08 or less. In addition, a Fisher's Exact p-value will also be computed to test this hypothesis.

In this analysis, each knee will be considered as a separate case, and unilateral and bilateral subjects will be analyzed together, providing the unilateral and bilateral groups are poolable per sensitivity analyses given in Section 3.1.5°.

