3.1.3. KNEE SOCIETY ASSESSMENT (PAIN) SCORE

The mean Knee Society Assessment score (KSSA) for the Cementless group is non-inferior to the mean KSSA for the Control group using a 6.4-point margin of non-inferiority. This test will be based on the upper bound of a one-sided 95% confidence interval for the difference, Control minus Cementless, of means at 22+ months. A conclusion of non-inferiority is supported if the upper bound of the confidence interval is 6.4 or less.

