3.3 SAMPLE SIZE JUSTIFICATION

In order to calculate the sample size for this study, the sample size needed to obtain 90% power for each primary endpoint was calculated. The endpoint requiring the largest sample size to maintain 90% power was Radiographic Success. Therefore, this is the sample size used in this study to ensure that we have a sufficient number of knees/patients to test each of the four primary endpoints with at least 90% power.

The sample size for the radiographic success primary endpoint was calculated as follows:

Let p_I and p_C denote the true population proportions of a successful outcome in the Cementless and Control groups, respectively.

Under H_0 , p_C is markedly larger than p_I and the Cementless device is inferior. Contrarily, under H_1 , this is not true and the true proportion of success for the Cementless device is, at worst, δ less than for the Control. We have δ = 0.08 (i.e., 8%).

Information about plausible values of the proportions p_I and p_C is available in the SSED for the LPS Flex Mobile Device (PMA #P060037). This document was used to help estimate the percentage of radiographic success for sample size purposes because it used a similar radiographic success/failure endpoint as the one given in this protocol. For purposes of the sample size calculation, we use the radiographic failure rates in Table 5 (page 18-19) of the document. This shows a 1.2% radiographic failure rate for the investigational device and a 2.4% radiographic failure rate for the control. Since we have slightly different radiographic success criteria, and because we want to ensure that we have adequate power for testing this endpoint, we will use 5% as our estimate of radiographic failure, giving a 95% estimate of radiographic success.

Assuming 95% to be the true, equal values of p_1 and p_2 , non-inferiority sample size calculations were implemented in nQuery Advisor 7.0 software using a 2:1 ratio of Cementless to Control subjects. This software uses methodology as described in an article by Farrington and Manning^e.

Definitions:

 p_l : Proportion of successes in the Experimental (Oxford Cementless) treatment group.

 $p_{\mathcal{C}}$: Proportion of success in the Control (Oxford Cemented) treatment group.

For a specified constant, $0 < \delta < 1$, the hypotheses of non-inferiority are:

$$H_0: p_C - p_I > \delta \text{ vs. } H_1: p_C - p_I \leq \delta.$$

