Type I error: conclude that the difference p_C - p_I is less than δ when in fact the difference is greater than or equal to δ , *i.e.* conclude that the experimental treatment is non-inferior to the control treatment when the control treatment is actually substantially better.

Statistics in Medicine 9(1990) pp 1447-1454.

^eFarrington and Manning

[&]quot;Test statistics and sample size formulae for comparative binomial trials with null hypotheses of non-zero risk difference for non-unity relative risk".

Type II error: conclude that the difference is greater than or equal to δ when it is actually less than δ , *i.e.*, conclude that the experimental treatment is inferior to the control treatment when the experimental treatment is essentially just as good.

Assumptions:

$\alpha = 0.05$	Probability of Type I error
$\beta = 0.90$	Probability of Type II error: power = $1 - \beta$
$p_{C} = p_I = 0.95$	Estimated success rate for control and treatment groups
δ = 0.08	Non-inferiority Margin

Resulting sample sizes (number of knees), not adjusted for attrition, are 191 Cementless device vs. 96 Control (5% type I error rate, 90% power). We increase our sample size by 10% to allow for possible exclusions in the primary analysis due to bilateral patients who may not be poolable with the unilateral cases, as well as attrition of up to 15%. This gives a sample size of 383 total subjects (255 Cementless vs. 128 Control).

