3.5.5. MISSING DATA, SENSITIVITY ANALYSES AND ACCOUNTABILITY TABLES

Data will be considered "missing" for a given primary endpoint if this endpoint cannot be calculated or is not available for a subject. If the subject has had a device failure or a UADE at any point or prior to their 22+ month outcome, they will not be considered as missing data for the Absence of Revision/Removal/UADE endpoint, as this endpoint is cumulative. A subject who has had a revision prior to two years will be considered a radiographic failure at the two - year time point for purposes of the primary analysis. When possible (i.e. the subject is seen by a study investigator in a non-emergency situation and collection of the data will not cause undue burden), Knee Society Scores will be collected for these subjects before the revision is performed in order to prevent these patients from missing knee scores in the primary efficacy analyses. A "worst case" score of twelve will be given for any Knee Scores that cannot be collected prior to the revision procedure. As an attempt to minimize missing data from the remaining primary endpoints, a nextobservation-carried-backward approach will be used to impute values for subjects missing data. Under this approach, if a primary endpoint is missing at the 24 month visit, the subject's next observation post 24-months will be used to impute a 22+ month outcome for that subject, for that particular endpoint. If no data is available after 2 years to carry backward for the missing data point, the subject's latest observation pre-24months will be carried forward to impute values for the missing 24 month visit.

Sensitivity analyses will examine the sensitivity of the results to missing values of the primary outcomes using a tipping point analysis, a best-case analysis, a worst-case analysis, and an analysis that imputes missing data with the last observation carried forward. If sensitivity analyses do not agree and we have more than 15% of values missing in either group, the method of Multiple Imputation may be used to further investigate the sensitivity of results to the missing data.

Accountability tables will be generated to show, at each study visit, the number of subjects who might be expected to attend a given visit and the number and proportion who did attend. Rows of the table will show counts for subjects contributing all data needed to

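### No missing-at-random estimate of the two-year knee-score difference is guaranteed: missing scores are filled by carrying, and multiple imputation is optional and gated at the attrition ceiling

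*Combined protocol and SAP*

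**What the plan says.** **Primary handling.** Section 3.5.5 fills a missing 24-month endpoint first with the next observation after 24 months. If there is none, the patient's "latest observation pre-24months will be carried forward to impute values for the missing 24 month visit". Section 3.5.2 admits such values to the primary Per Protocol analysis. For a revised knee whose score could not be taken before revision, a fixed score of 12 is used instead.

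**Checks.** Section 3.5.5 lists four sensitivity analyses: tipping point, best case, worst case, and "an analysis that imputes missing data with the last observation carried forward".

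**Multiple imputation.** It requires that these analyses disagree and also that "we have more than 15% of values missing in either group, the method of Multiple Imputation may be used".

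**Attrition.** Section 3.3 enlarges the sample for bilateral patients who may not be poolable "as well as attrition of up to 15" per cent.

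**Test.** Section 3.1.3 uses the "upper bound of a one-sided 95% confidence interval for the difference, Control minus Cementless, of means at 22+ months", with a margin of 6.4 points. Section 3.1.4 does the same for the Function score with 9.2 points. Section 3.1 requires all four co-primaries to succeed.

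**The concern.** A carried-forward score records the device difference at an earlier visit, not at two years. If that difference grows, each such score pulls the estimate of Control minus Cementless towards zero. In a superiority trial this dilution is usually conservative. In a non-inferiority trial it favours the claim.

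The listed carry-forward check cannot expose this, because it departs from the primary rule only for patients who have a later visit. Follow-up ends when the last patient completes two years, so late enrollees have little or no later follow-up to carry back, and patients who leave the study for good have none. Imputation from the patient's own earlier scores would address the problem, but it sits behind two joint conditions and remains discretionary when both are met.

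Section 4.3 lists loosening from failed biologic fixation and from hydroxyapatite particles as potential risks, so a late-opening gap is conceivable. No section gives an expected score trajectory.

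**Working it through.** **1. The plan's own figure.** Inputs from Section 3.3: "5% type I error rate, 90% power", 2:1 allocation, success 0.95 in both arms, margin 0.08. By the unpooled normal formula, control n = (1.645 + 1.282)² × (0.95×0.05 + 0.95×0.05/2) / 0.08² = 8.564 × 0.07125 / 0.0064 = 95.3, so 96. Cementless n = 2 × 95.3 = 190.7, so 191. Both match. (The Farrington–Manning version gives 94 and 188.) Inflation: 191/(1 − 0.10 − 0.15) = 254.7, so 255; 96/0.75 = 128; total 383. This matches exactly, so 15% attrition is built into the sample size.

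**2. When the 15% condition is met.** Taking 10% off for bilateral patients, who leave the primary knee-score analysis (Section 3.5.2), leaves about 230 and 115. Since 0.15 × 230 = 34.5 and 0.15 × 115 = 17.25, up to 34 and 17 missing scores do not meet it. The probability that at least one arm exceeds 15% (independent binomials) is:

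| True missing rate | Probability |
|---|---|
| 8% | 0.5% |
| 10% | 4.5% |
| 12% | 22% |
| 15% | 73% |

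The plan does not say whether missing values are counted before or after carrying.

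**3. A simple bound on the dilution.** The plan gives no knee-score SD. Having 90% power with 96 controls implies at most 6.4 × √(96/1.5) / 2.926 = 17.5 for Assessment and 9.2 × 8 / 2.926 = 25.2 for Function. Suppose a share f of scores is carried, those scores show no arm difference, and the true difference equals the margin m. Then the error rate is Φ(m·f/SE − 1.645), with SE = SD × √(1/230 + 1/115).
- Assessment, f = 0.15, SD 17.5: SE = 2.00, Φ(0.96/2.00 − 1.645) = 12%.
- Assessment, f = 0.15, SD 10: SE = 1.14, Φ(0.96/1.14 − 1.645) = 21%.
- Assessment, f = 0.05, same SDs: 7% to 9%.
- Function, f = 0.15, SD 25 to 15: 12% to 20%.

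**4. Simulation for the Assessment score.** Assumed, none of it in the plan: SD 16, visit correlation 0.6, dropout related to earlier scores at about 5% per interval (1 − 0.95³ = 14.3%), true two-year deficit 6.4. Gaps are at 6 weeks, 6 months, 1 year and 2 years. Entries are the rate of falsely declaring non-inferiority.

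| Gap pattern | Carrying, no later visits | Carrying, half of missing have a later visit |
|---|---|---|
| 0, 2, 4, 6.4 | about 9% | about 7% |
| 0, 0, 0, 6.4 | about 12% | about 7% |
| 6.4 throughout | about 4–5% | – |
| 10, 9, 8, 6.4 | about 2% | – |

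Multiple imputation by arm stayed at 4–6% throughout. Other simulated dropout models with no later visits gave 6.6% to 10.0% for the gradual gap and 10.1% to 12.4% for the late one, and 7.1% and 7.8% when half had a later visit. Monte Carlo error is up to about one point with 1,000 trials. The mechanism is visible in the mean: with a gap only after one year, the expected carried estimate is 6.4 × 0.857 = 5.5, against 5.44 to 5.48 simulated.

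**The case against.** **Multiple imputation may well be reached.** A reader might infer that it never runs at planned attrition. The documents do not support that: the condition applies to either group, so at a true 15% at least one arm exceeds the threshold about 73% of the time. Disagreement among the checks is also likely. Taking worst case as 12 for Cementless and 100 for Control (an assumption; the plan does not define it), it failed in every falsely non-inferior trial of one simulation, and both conditions were met in about 69% of false positives under a widening gap. This stands against *never*. It does not create a guarantee, because use remains optional and 15% is a ceiling: at a true 10% the threshold is passed only 4.5% of the time.

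**Other checks run at any missing rate.** The tipping-point, best-case and worst-case analyses do not rest on carry-forward. That is correct, but they are bounds. At 14.3% missing, the worst case above contributes 0.143 × 88 = 12.6 points even with identical devices, so it fails whether or not the device is inferior. The tipping-point analysis is more useful, but its details are not specified.

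**Most scores are observed.** A reader might infer that the knee-score results as a whole rest on carrying. At planned attrition at least 85% of scores are observed; moving the Assessment difference by a full margin would take an error of 6.4/0.15 = 42.7 points in the carried share. The error rates above already reflect this.

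**The carry-forward check is not a duplicate.** This stands: it differs wherever a later score was carried back, and so tests that step.

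**Further safeguards.** The ITT analysis (Section 3.4.2) aims to assess missing data, mean scores are compared by visit (Section 3.5.4), and revised knees take a pre-revision score or 12. These help reveal a widening gap; none specifies a missing-at-random estimate against the margin.

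**All four endpoints must succeed.** So a knee-score false positive is not by itself a study false positive. But the 5% study-wide claim in Section 3.1 relies on each test holding 5%. If the device is clearly acceptable on the other three, the weak test sets the study's error rate.

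**Conclusion.** The point holds as a gap in the plan. The primary knee-score analysis uses single-value carrying, and no missing-at-random estimate is guaranteed at any missing rate. The possible effect is false non-inferiority of about 9–12% instead of 5% when the gap widens and no missing patient has a later visit, or about 7% when half have one. This rests on the assumed SD, correlation, dropout and trajectory. With a constant gap there is no inflation, and with a narrowing gap carrying is conservative. The documents therefore do not show that the primary result will be biased, only that it would be in the unfavourable direction under a plausible pattern. The same rules also fill missing radiographic outcomes; that effect was not quantified. This is a change the sponsor should make, not a fatal flaw.

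**What to change.** In Section 3.5.5, delete the 15% condition, the disagreement condition and the optional wording. For both Knee Society scores, always report the 24-month difference from multiple imputation by arm, or an equivalent repeated-measures model, using the pre-operative and all post-operative scores. Keep the score-of-12 rule for revised knees. Compare the one-sided 95% upper bound with 6.4 and 9.2 points, beside the primary result.

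Keep the last-observation-carried-forward analysis as a check on the carry-backward step. Making imputation the primary method is optional.

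The cost is SAP wording, some programming and slightly wider intervals. The Schedule of Events (Section 2.7.1) already collects the scores pre-operatively and at every follow-up visit, so no new data, visits or patients are needed.

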3.5.6. EXPLORATORY ANALYSES OF THE PRIMARY OUTCOME INCLUSING CENTER EFFECTS

The association between each primary endpoint and device group at 22+ months across sites will be examined using either an analysis of variance (continuous endpoint) or the Breslow-Day test for homogeneity of odds ratios (binomial endpoint). Sites with less than or equal to 5 cases in either treatment will be combined to form a "pooled" site for analysis. A significant p-value indicates heterogeneity of odds ratios of clinical success across sites, and in this case the proportions of success for each site will be examined graphically and descriptively to assess site dependency.

In addition, the association between device group and each primary endpoint for unilateral and bilateral subjects will be examined using either an analysis of variance or the Breslow-Day test for homogeneity of odds ratios. The test for center effects will use a p-value of 0.05. If there is no evidence of treatment*center interaction ($p \ge 0.05$), data will be pooled across centers. However, the existence of a quantitative interaction between treatment and center does not necessarily invalidate the analysis in pooling data across centers. Thus, if p < 0.05 then the observed proportions for each site will be examined graphically to assess site dependency as well as whether or not a qualitative interaction exists. Further, the sites contributing to this interaction will be examined, and if necessary, a stratified analysis will be conducted and results compared to overall study results to assess consistency.

Patient covariates in the proposed statistical modeling below include age at time of surgery, gender, primary diagnosis, unilateral vs. bilateral status, preoperative Knee Society Assessment Scores, Knee Society Function Scores, use of pain medications and study site. Others may be added if other covariates potentially affecting the outcome are observed. To determine the effect of these covariates on the primary endpoints, separate regression models will be used. In the regression models, the dependent variable will be the primary study endpoint; thus a logistic regression model will be needed for the binary study endpoints. The model will also include device group (control or experimental) as an independent variable and the above baseline and demographic variables listed above as covariates. A graphical examination of the residuals will be performed to assess the model assumptions. To determine whether a covariate has an effect on the primary study outcomes, a Type 3 analysis of effects based on the Wald Chi-square test will be conducted.

^f Gail, M.H., and Simon, R. "Testing for qualitative interactions between treatment effects and patient subsets." *Biometrics*, 1985, **41**, 361-272,

4.0 RISK ANALYSIS

This investigation is designed to collect data on a new mobile bearing partial knee system. The Oxford® Cementless Partial Knee System is intended to help the patient gain mobility and decrease pain. Risks associated with this knee system include general surgical and partial knee arthroplasty risks. Due to the investigational nature of the system, there may be risks that are unknown.

4.1. GENERAL RISKS ASSOCIATED WITH SURGERY

As with any surgical procedure, there are risks involved with partial joint replacement surgery. Potential adverse events include, but are not limited to:

- 1. Complications resulting from anesthetic
- 2. Damage to nerves and blood vessels
- 3. Allergic reactions to the metallic devices
- 4. Phlebitis
- 5. Long-term swelling
- 6. Pulmonary embolus
- 7. Delayed wound healing
- 8. Prolonged illness
- 9. Hematoma
- 10. Wound dehiscence and/or drainage
- 11. Excessive bleeding that may result in the need for blood transfusions and/or further surgery
- 12. Permanent pain, deformity; and inconvenience.
- 13. Permanent Brain Damage
- 14. Pneumonia
- 15. Venous Thrombosis
- 16. Heart Attack
- 17. Kidney Failure

4.2. GENERAL RISKS ASSOCIATED PARTIAL KNEE REPLACEMENT

- 1. Early or late infection perhaps necessitating device removal
- 2. Component dislocation
- 3. Fracture or perforation of the bone or device (intraoperative or post-operative)
- 4. Device loosening or migration
- 5. Valgus/Varus deformity
- 6. Inadequate lubrication
- 7. Patellar tendon rupture and ligamentous laxity
- 8. Fretting or corrosion of implant interfaces
- 9. Wear and/or deformation of articulating surfaces
- 10. Particulate wear debris may initiate a cellular response leading to osteolysis
- 11. Damage to surrounding tissues, cartilage, or tendons
- 12. Inadequate range of motion
- 13. Persistent pain

- 14. Progression of the disease in the lateral compartment necessitating revision
- 15. Transient peroneal palsy secondary to surgical manipulation and increased joint movement
- 16. Implantation of the device may require greater surgical exposure and prolonged surgical time
- 17. Instability
- 18. Peripheral neuropathies, heterotopic bone formation and/or histological reactions which may occur with or without clinical significance
- 19. Failure of cement fixation resulting in loosening of the implant

Rarely some adverse events may be fatal. These possible adverse events are not unique to the Oxford® Cementless Knee System and, as stated above, may occur with any partial joint replacement surgery.

Limitations may be imposed depending upon the patient's age, general health, baseline (preoperative) activity level and baseline (preoperative) condition of the knee and other joints.

4.3. POTENTIAL RISKS ASSOCIATED WITH OXFORD® CEMENTLESS PARTIAL KNEE SYSTEM REPLACEMENT

The safety and efficacy of the Oxford® Cementless Knee System has not been demonstrated clinically, and patients participating in the study may be subject to increased risks and/or adverse events, in addition to those listed under general surgical risks, including, but not limited to:

- 1. Excessive wear and loosening of implants due to migration of hydroxyapatite particles into the joint space
- 2. Failure of biologic fixation resulting in loosening of the implant

4.4. MINIMIZATION OF RISK

With the increased understanding of failure modes for mobile bearing knees, pre-clinical testing and clinical results found in the literature, it is believed that none of the previously mentioned adverse events will occur in significant numbers. This investigational plan has reduced the potential risk to the patient through the following methods:

- 1. By defining a patient population that limits the exposure of the device to patients conforming to the proposed indications, exclusions, and age requirements
- 2. By utilizing surgeon investigators who are licensed orthopedic surgeons that are trained in the usage of the Oxford® Cemented Partial Knee, thereby reducing surgical-related risk
- 3. Developing a surgical technique that may help eliminate potential operative difficulties

Prior to deciding whether to participate in the investigation, each subject will be provided with a description of all known potential complications and increased risks. Patients will also be provided with a description of alternate treatments. With this information and the counsel of their physician, patients will decide whether participation in the investigation and potential use of

the investigational device is in their best interest. The provision of this information and the patients' consent to participate in the investigation will be documented through the use of an Informed Subject Consent form.

Only licensed orthopedic surgeons who are practiced in partial knee replacement surgical procedures will be allowed to participate as clinical investigators for this investigation. General surgical risks will be controlled by surgeon adherence to accepted surgical guidelines and procedures. Risks related to the prosthetic design will be controlled by device labeling, and the investigators' adherence to the instructions for its safe handling and use.

The sponsor will further minimize the identified and/or emergent risks throughout the investigation by requiring the clinical investigators to document and report all complications and adverse effects to the investigation sponsor. Any unanticipated adverse device events will be reported to each clinical investigator, reviewing Institutional Review Board (IRB) and to the FDA. Based upon an evaluation of such events, the sponsor may either amend the investigational plan or terminate the investigation to protect the rights, safety and welfare of the subjects. Should an IRB decide to suspend or withdraw its approval for a clinical investigator to conduct the investigation at that institution based on unacceptable risks to the investigational subjects, the investigation sponsor will notify all reviewing IRBs, clinical investigators and the FDA of this action. To further minimize risks, any new information obtained during the course of the investigation relating to risks to the patient will be provided to subjects, investigators, and IRBs.

The investigation has been designed to minimize the number of patients exposed to the investigational device, yet provide sufficient numbers of subjects for valid scientific analysis of the compiled investigation data. The risks will be further controlled by the investigational design, the procedures for monitoring the dispensing of the investigational devices to the investigation subjects and the documentation, reporting and evaluation of the results from its surgical use.

The potential risks to the subjects in this investigation have been further minimized by the extensive preclinical and laboratory testing performed by the sponsor to verify the design requirements and the suitability for the intended use. Use of the investigational device is further supported by the reports from the medical and scientific literature for similar devices and the manufacturing processes and controls used to manufacture the prosthesis.

